### **Baseline Characterization:**

All subjects will have a basic psychiatric diagnostic evaluation done to gather a thorough developmental, medical, and psychiatric history, as well as complete a physical and mental status exam. The medical history and exam will be aimed at ruling out other medical conditions that could exacerbate anxiety or behavioral symptoms (e.g., chronic gastrointestinal disease, obstructive sleep apnea, thyroid disease). The following standardized scales and testing will also be conducted.

1. **Autism Diagnostic Interview-Revised (ADI-R).**
2. **Anxiety Disorders Interview Schedule (ADIS-IV).** The ADIS-IV (Silverman & Albano 2004) consists of semi-structured interviews for children and parents organized diagnostically to permit differential diagnoses among the DSM-IV anxiety disorders. It also includes questions on mood and externalizing disorders. We expect that not all child questions will be answerable depending on the communication abilities of the child. However, this will still provide information about the usefulness of this instrument in future trials involving children with PDD.
3. **Stanford-Binet Intelligence Scales, Fifth Edition (SB5).** The SB5 (Roid 2003) will be used to calculate an abbreviated battery IQ. The abbreviated IQ was chosen in order to

limit subject burden given that a number of other measures will be conducted at screening.

4. **Peabody Picture Vocabulary Test, Fourth Edition (PPVT-4)**. The PPVT-4 (Dunn & Dunn 2007) will be done to assess receptive language skills.
5. **Vineland Adaptive Behavior Scales, Second Edition (Vineland II)**. The Vineland-II (Sparrow et al 2005) will be used to assess adaptive functioning in four domains: Communication, Daily Living Skills, Socialization, and Motor Skills. This is a well-standardized open-ended interview used to assess the overall functioning of children and adults. This measure is especially important for subjects with PDDs given that their intellectual level is not always comparable to their adaptive functioning (Volkmar et al., 1993).
6. **Laboratory evaluation**. This will consist of a complete blood cell count with platelets and differential, a comprehensive metabolic panel (including electrolytes, renal function tests, liver function tests, glucose), and thyroid function tests. These tests will be drawn to rule-out any occult medical problems not detected by history and physical exam alone. A urine pregnancy test will be obtained from females of childbearing potential.

#### **Mirtazapine/Placebo Treatment:**

Subjects will receive 7.5 mg of mirtazapine nightly at the start of the trial. The dose will be increased by 7.5 mg per week for subjects with weights less than 50 kg and by 7.5 or 15 mg per week for subjects weight greater than 50 kg depending on efficacy and tolerability. During the first 6 weeks, patients will be seen bi-weekly with additional telephone visits conducted in between clinic visits for additional monitoring of adverse effects and for dosing adjustment as necessary. The optimal dose will be reached by week 6 of treatment. A final visit will be conducted at week 10 with a follow up phone call at week 8. The minimum starting dose will be 7.5 mg and the maximum total daily dose will be 45 mg (based on our preliminary study and clinical use). Medication will be dosed once or twice daily depending on response and tolerability. Our previous experience has found the addition of a morning dose to be well-tolerated and effective in a clinical sample (Posey et al 2001). Once daily dosing at night only will be allowed if children are unable to tolerate a morning dose due to sedation.

Matching placebo prepared by a compounding pharmacy will be identical to mirtazapine in appearance and taste.

#### **Outcome Measures:**

1. **PARS**. The PARS will be the primary outcome measure. It will be conducted at screening, baseline, and each follow-up visit.
2. **Screen for Childhood Anxiety Related Emotional Disorders (SCARED)**. The SCARED (Birmaher et al 1999) is a 41-item scale that includes both a child/self-report and parent-report form. It assesses symptoms of panic disorder, separation anxiety disorder, social phobia, and generalized anxiety disorder, as well as school avoidance. It will be conducted at baseline and each follow-up visit.
3. **Child and Adolescent Symptom Inventory (CASI) Anxiety Items**. These include 20 parent-rated items from the Child and Adolescent Symptom Inventory that has been administered to children with PDD in previous trials (Sukhodolsky et al 2008). It will be conducted at baseline and each follow-up visit
4. **Aberrant Behavior Checklist (ABC)**. The ABC is a 58-item questionnaire with 5 subscales derived by factor analysis: Irritability, Social Withdrawal, Stereotypy, Hyperactivity, and Inappropriate Speech (Aman et al., 1985). It has been extensively used in psychopharmacological studies of autism and assesses many symptoms that are either central to autism (Social Withdrawal, Stereotypy, Inappropriate Speech) or

frequently a target of treatment (Irritability). It will be conducted at baseline and each follow-up visit.

5. **Children's Sleep Habit Questionnaire (CSHQ).** The CSHQ (Owens et al 2000) is a 46-item parent-report questionnaire that assesses bedtime resistance, sleep onset delay, sleep duration, sleep anxiety, night waking, parasomnia, sleep disordered breathing, and daytime sleepiness that has been used in children with PDD (Honomichl et al 2002). It will be conducted at baseline and each follow-up visit.
6. **Clinical Global Impressions (CGI).** A trained clinician blind to treatment assignment and detailed side-effect information will perform the CGI. The CGI is designed to take into account all factors to arrive at an assessment of severity and response to treatment, including parent report, parent-rated measures, teacher-rated measures, and clinician-rated measures (as described below). The CGI Severity (CGI-S) item is rated on a scale from 1 to 7 (1 = normal, not at all ill; 2 = borderline ill; 3 = mildly ill; 4 = moderately ill; 5 = markedly ill; 6 = severely ill; 7 = among the most extremely ill patients). The CGI Global Improvement (CGI-I) item is also rated from 1 to 7 (1 = very much improved; 2 = much improved; 3 = minimally improved; 4 = no change; 5 = minimally worse; 6 = much worse; 7 = very much worse). Subjects receiving a CGI-I rating of 1 or 2 will be classified as **responders** to treatment. The severity ratings will be conducted at baseline and the last follow-up visit. The improvement ratings will be conducted at each follow-up visit.
7. **Developmental Disability-Child Global Assessment Scale (DD-CGAS).** The DD-CGAS (Wagner et al 2007) is a modified version of the CGAS for use in PDD treatment trials. It will be conducted at baseline and at the last follow-up visit.

### **Safety Monitoring:**

Adverse events, vital signs, height, and weight will be collected at each clinic visit. A Comprehensive Metabolic Profile and CBC will be collected at baseline and endpoint. Standard methods and precautions will be used to protect the venipuncture site from bleeding and infection. In addition, a trained pediatric phlebotomist will perform all venipunctures that are required. A research assistant, who will be familiar with the subjects, will accompany the subject and their parents for the venipuncture. Parents are encouraged to remain with the subject at all times. To minimize the subject's anxiety and phobic reactions, we "talk through" the procedure with the subject so that they might know, to some extent, what to expect. For subjects who are minimally verbal, we use visual supports in order to prepare the participants for the blood draw. Topical anesthetics (e.g., EMLA or lidocaine cream) are sometimes used as well at the discretion of the nurse or investigator.

Adverse events will be collected via a structured side effect rating scale completed with the participant and their primary caregiver. This will include a list of side-effects that have been reported with mirtazapine at a rate greater than 1% including sedation, sleep disturbance, dry mouth, increased appetite, nausea/vomiting, constipation, dyspnea, urinary frequency, back pain, edema, myalgia, dizziness, weakness, tremor, irritability, abnormal dreams, abnormal thinking, and confusion. Weight gain is a potential side effect especially in those subjects that have been on atypical antipsychotic medications which can also cause weight gain. Parents of the subject will be informed of this risk in the informed consent prior to participation in the study. Each of these side-effects plus any additional complaints will be rated at baseline on a 4-point scale by the caregiver as follows: 0 = none; 1 = mild; 2 = moderate; 3 = severe. This scale is similar to that used by the RUPP Autism Network (Aman et al., 2005). Suicidality will be assessed at each visit by directly asking the subject (when verbal skills are sufficient) and caregiver about any thoughts or behaviors that directly or indirectly might indicate suicidality (e.g., morbid thoughts, self-injury, statements about life not being worth living), when indicated by positive responses. At baseline, the Columbia-Suicide Severity Rating Scale (C-SSRS) will be administered per the instructions at [www.cssrs.columbia.edu/clinical\\_trials.html](http://www.cssrs.columbia.edu/clinical_trials.html). The C-

SSRS will also be administered at each subsequent visit following the first report of suicidality. Subjects and caregivers will also have information on how to contact the on-call physician from our practice group who provides coverage 24 hours/day and 365 days/year. Physicians taking call are familiar with research protocols and can contact the principal investigator at any time.

All adverse events picked up on the rating scale as new will be recorded by the physician. The physician will also ask about any visits to the doctor, new medication use (e.g., OTC cold medicine), or any other complaints, in order to be confident that most AEs are uncovered. The physician will keep a running log of adverse events that will record the date of onset, date of resolution, seriousness, severity, and relationship to study intervention (e.g., definite, probable, possible, remote, or none) as well as whether the adverse event led to a change in study intervention or other treatment.

A physician will review vital signs and laboratory data, as they become available. All significant AEs as well as the progress of the study will be reviewed and discussed in detail at the biannual meetings of the **Lurie Center Data and Safety Monitoring Board (DSMB)**. Special attention will be made by the treating physician to note all weight gain trends and bring any concerns to the DSMB. The DSMB is currently being formulated for the Lurie Center and will include rotating members of the Lurie Center including pediatricians, pediatric and adult neurologists, child and adolescent psychiatrists and independent members outside the Lurie Center.

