## **B. IMPACT AND RELEVANCE:**

PDDs are severe childhood-onset disorders which cause significant impairment in social interaction, communication, and behavior. The most common PDDs are autistic disorder, Asperger's disorder, and PDD not otherwise specified (NOS). These disorders affect 1 in 88 persons and lead to substantial impairment and disability.

Our group and others have been actively conducting clinical trials aimed at treating both core and associated symptoms of the disorder. Risperidone was approved by the FDA for the treatment of irritability in children and adolescents with autistic disorder. This approval was based in large part on studies conducted by the National Institute of Mental Health (NIMH)-funded Research Units of Pediatric Psychopharmacology Autism Network which included our center and four other academic sites (RUPP Autism Network 2002). Our group has also been involved with clinical trials aimed at finding better approaches to the treatment of hyperactivity co-morbid with PDD (Posey et al 2006b; Posey et al 2007; RUPP Autism Network 2005).

Interfering repetitive behavior and other symptoms that resemble obsessive-compulsive disorder (OCD) have also been studied in PDD. These symptoms are often treated with selective serotonin reuptake inhibitors (SSRIs) which work relatively well in adults with autism (McDougle et al 1996a). In children, however, their efficacy has been less robust and the frequent occurrence of activating side-effects is problematic (Posey et al 2006a).

This potential for activating side-effects with SSRIs was recently confirmed by a large multi-site clinical trial sponsored by the National Institutes of Health. In this trial from the Studies to Advance Autism Research and Treatment (STAART) network, 149 children and adolescents (ages 5-17 years) were randomized to flexible dose treatment with either citalopram (dose range 2.5-40 mg; mean dose 16.5 mg) or placebo (King et al 2009). Citalopram was no better than placebo on measures of global outcome and repetitive behavior, and was associated with adverse effects including hyperactivity, increased energy level, impulsivity, and gastrointestinal symptoms.

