In addition to evidence for the efficacy of mirtazapine in treating anxiety and other symptoms relevant to PDD, its effects on the serotonin system may also be important. Serotonergic abnormalities are well-known in autism and include elevations of whole blood serotonin (Schain & Freedman 1961; Anderson et al 1987), abnormal neuroendocrine responses to pharmacological probes of the 5-HT system (Hoshino et al. 1984; McBride et al. 1989), and worsening of behavioral symptoms in autistic adults after acute dietary depletion of tryptophan (McDougle et al. 1996b).

Our group was the first to report on the efficacy of mirtazapine in PDD (Posey et al 2001). We found it helpful for a variety of symptoms associated with PDD. One limitation of this study was that it was retrospective and so did not have uniform entry criteria, treatment or assessment. Furthermore, the subjects in the retrospective study had failed multiple other adequate medication trials (mean # previous trials=6). Thus, they were clearly treatment-resistant and not representative of the majority of persons with PDD. The response rate compared favorably to that of SSRIs that examined response rate retrospectively and over a longer period of time (Branford et al 1998). Since the publication of that first study, our group and others (Albertini et al 2006; Coskun & Mukaddes 2008, Nguyen & Murphy 2001) have continued to find it useful for a variety of symptoms including anxiety, insomnia, irritability, and hyperactivity dosing it both daily and twice daily.

In summary, anxiety frequently occurs in PDDs yet no treatment studies have been conducted which can guide treatment. SSRIs, which are frequently used to treat anxiety in children without PDD, cause an unacceptably high degree of activating side-effects.

Mirtazapine appears promising in the treatment of pediatric anxiety disorders and PDDs. A prospective, pilot study is urgently needed to address this large gap in treatment knowledge. This project is extremely relevant to advancing the knowledge about autism and its treatment. This proposal will fully characterize a cohort of children and adolescents with PDD and interfering anxiety. Each participant will then be randomized to either mirtazapine or placebo under double-blind trial conditions.

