### **Exclusion Criteria:**

1. **Diagnosis of Rett's disorder or childhood integrative disorder.** Subjects with these other PDDs will not be enrolled since these disorders have a different etiology, course, and treatment response.
2. **Diagnosis of OCD, post-traumatic stress disorder, major mood disorder, psychotic disorder, or substance use disorder.** These disorders are exclusionary since the primary treatment of these disorders may require acute psychosocial treatments or other medications that would confound the assessments.
5. **Presence of any past or present medical conditions that would make treatment with mirtazapine unsafe.** This includes allergy to mirtazapine; agranulocytosis/bone marrow suppression; heart, kidney, or liver disease; unstable seizure disorder; and pregnancy (or being sexually active without using acceptable methods to prevent pregnancy).
3. **Use of other antidepressants or benzodiazepines.** Subjects will need to be off medications from these classes for at least 5 elimination half-lives prior to randomization.
6. **Use of other psychotropic medications which are ineffective, poorly tolerated, or sub-optimal in terms of dose.** A board certified child and adolescent psychiatrist will assess any other psychotropic medications being used and determine whether they are effective, tolerated, and optimal in terms of dose. Concurrent use of a psychotropic medication (other than antidepressants or benzodiazepines) will be allowed if the dose has been stable for 60 days and if they meet the above criteria of effectiveness, tolerability, and dose. Medications for concomitant attention-deficit/hyperactivity disorder symptoms (e.g., stimulants), insomnia (e.g., melatonin), and irritability (e.g., atypical antipsychotics) will be allowed if they meet the above criteria. Any medication that is assessed as possibly contributing to the subject's anxiety symptoms will not be allowed.
7. **Use of linezolid (Zyvox).** Subjects will need to refrain from taking linezolid during the study to prevent a potential drug interaction related to the serotonin syndrome. Linezolid taken in conjunction with mirtazapine could increase the risk of increasing serotonin activity to toxic levels, causing what is known as serotonin syndrome. This syndrome is characterized by at least 3 of the following symptoms: agitation, diaphoresis, diarrhea, fever, hyper-reflexia, incoordination, myoclonus, shivering, or tremor.

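### The prompted side-effect list omits the activating effects that motivate the trial, so activation as an adverse event rests on open questions without a systematic baseline rating

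*Combined protocol and SAP*

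**What the plan says.** **Rationale (section B, Impact and Relevance).** The citalopram trial cited there found no benefit over placebo, and the drug "was associated with adverse effects including hyperactivity, increased energy level, impulsivity, and gastrointestinal symptoms". The section's summary says that SSRIs "cause an unacceptably high degree of activating side-effects". Mirtazapine is presented as a drug that seldom produces activation. Safety and tolerability are part of the first specific aim in section A.

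**Elicitation (section E, Safety Monitoring).** Adverse events are collected at each clinic visit with a structured scale completed with the participant and caregiver. On its content the plan says: "This will include a list of side-effects that have been reported with mirtazapine at a rate greater than 1" per cent. The list opens with seven effects ("including sedation, sleep disturbance, dry mouth, increased appetite, nausea/vomiting, constipation, dyspnea") and goes on to name eleven more, among them tremor and irritability. The caregiver rates these, and any further complaints, from 0 (none) to 3 (severe). The sentence describing that rating mentions baseline only. The physician logs what the scale shows to be new, and also asks about doctor visits, new medicines and other complaints.

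**Analysis (section E, Statistical Analysis Plan).** The occurrence of particular adverse effects, not named, is compared between arms with Chi-square tests. The Aberrant Behavior Checklist (ABC) is given at baseline and weeks 2, 4, 6 and 10, and falls under the mixed model for continuous measures.

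**The concern.** The items prompted one by one were chosen because they are already known for mirtazapine. That rule cannot show whether the SSRI-type effect that motivates the trial also occurs with this drug in this population. Sedation and appetite are asked about by name. Hyperactivity, increased energy and impulsivity are recorded as adverse events only if they surface in answer to an open question.

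Two things are at stake. First, the recorded incidence of activation is likely to be too low in both arms, and a table that places it beside sedation would compare figures gathered in different ways. Second, an event is logged from the scale when it is new, which presupposes a baseline rating. A behavior without its own row has one only if the caregiver happens to raise it at baseline. The exclusion criteria allow children on stable stimulants for attention-deficit/hyperactivity symptoms, so worsening of existing hyperactivity is a realistic event for this scale to miss.

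The pilot is meant to inform a larger trial, and activation incidence is a figure that its planners would want.

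**Working it through.** The documents state no figure to reproduce. The check compares lists.

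**Step 1. Count the prompted items.** The first part of the list has 7 entries (sedation to dyspnea) and the second has 11 (urinary frequency to confusion): 7 + 11 = 18. The known mirtazapine effects in section B are the same 18.

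**Step 2. Match them to the effects named for citalopram in section B.**

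| Effect named for citalopram | On the prompted list? | Measured in structured form elsewhere? |
|---|---|---|
| Hyperactivity | No | ABC Hyperactivity subscale |
| Increased energy level | No | No subscale of that name |
| Impulsivity | No | No subscale of that name |
| Gastrointestinal symptoms | Partly (nausea/vomiting, constipation) | Not applicable |

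The activating effects score 0 of 3. The non-activating one is partly prompted. Irritability and sleep disturbance, which can accompany activation, are on the list.

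**Step 3. Follow an unlisted effect to the adverse-event log.** It can enter as a further complaint on the caregiver scale or through the physician's question about other complaints. Both are open questions, and neither guarantees a baseline value.

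**Step 4. Check whether the ABC fills the gap.** It supplies scores at five visits (baseline and weeks 2, 4, 6 and 10). It gives no onset date, severity grade or relationship to treatment, all of which the log requires, and nothing says that its scores are carried into the log. It is analyzed as a continuous score, and a mean can stay flat or improve while a minority of children worsen.

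**Step 5. Illustrate the effect of incomplete capture (assumptions only).** Let p be the true proportion of children with activation, c the fraction of cases that open questions bring out, and n = 20 on mirtazapine (Sample Size section). The chance of recording at least one case is 1 − (1 − pc)^20.

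| p (assumed) | c = 1 | c = 0.5 | c = 0.25 |
|---|---|---|---|
| 10% | 1 − 0.90^20 = 88% | 1 − 0.95^20 = 64% | 1 − 0.975^20 = 40% |
| 5% | 1 − 0.95^20 = 64% | 1 − 0.975^20 = 40% | 1 − 0.9875^20 = 22% |

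The documents support no particular p or c. The table shows only the direction, and how quickly a signal can be lost in an arm of 20.

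**Step 6. Consider the between-arm comparison.** If c is the same in both arms, the expected recorded difference is c × (p on mirtazapine − p on placebo). It shrinks toward zero but keeps its sign.

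**The case against.** The strongest reply is that activation is asked about, though not on this form. The ABC Hyperactivity and Irritability subscales are completed in both arms at baseline and at every follow-up visit, and differences between arms are examined. Irritability and sleep disturbance are prompted. The physician puts an active open question, so reporting is not purely volunteered. All of this is correct. It rules out a reading that a reader might be tempted to make: that low activation could be reported only because nobody asked. What remains is narrower and concerns adverse-event incidence, with its baseline, severity and attribution.

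The list is also introduced as something the scale includes, and the scale is described as similar to one used by a research network. The form itself is not in the documents and may hold more rows. That stands as a caveat. If the activation items are already there, the protocol need only say so.

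Third, both blinded arms are questioned in the same way, there is no SSRI arm, and neither the aims nor the efficacy indicators promise a comparison with SSRIs. Under-capture therefore costs the planned comparison sensitivity and does not favor either arm. This also stands. It does not help the within-arm incidence, or its comparison with prompted effects.

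Finally, a reader might infer that the list ought to be able to detect serotonin syndrome. The exclusion criteria say "This syndrome is characterized by at least 3 of the following symptoms" and name nine: "agitation, diaphoresis, diarrhea, fever, hyper-reflexia, incoordination, myoclonus, shivering, or tremor". Only tremor is prompted, so 1 of 9. But those signs appear solely to explain why linezolid is excluded. The protocol does not make the syndrome a monitoring target or give the checklist a diagnostic role, and hyper-reflexia is found on examination and cannot be rated by a caregiver. The documents do not support a criticism on that ground.

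**Conclusion.** The point holds in limited form. None of the three activating effects that motivate the trial is among the 18 prompted items. Activation as an adverse event therefore depends on open questions and lacks a systematic baseline rating, so its recorded incidence is likely to be too low in both arms and is not comparable with that of sedation or increased appetite. The ABC covers hyperactivity and irritability in part, as continuous scores.

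This rests on two assumptions: that the named list describes the form in use, and that open questions bring out fewer cases than named items do. The documents give nothing from which to size the second, so the capture fractions in the working are illustration and not evidence of how many cases would be lost. The plan does not hide activation, and its between-arm comparison is not biased toward mirtazapine. This is a cheap improvement to safety data collection in a 30-subject pilot, worth making because tolerability is part of the first aim.

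**What to change.** 1. In Safety Monitoring, add four items to the structured list: hyperactivity, increased energy, impulsivity and agitation. The first three are the effects named for citalopram. Agitation is a related behavior that the protocol names in its linezolid criterion.
2. State that every item is rated 0 to 3 at baseline and at each later visit. The rating sentence now mentions baseline only, while adverse events are collected at each visit.
3. In the Statistical Analysis Plan, name activation among the adverse effects compared between arms, defined as any of the four items new or worse than baseline.
4. Report change in ABC Hyperactivity and Irritability by arm beside it, as supporting safety data.
5. If the form already contains these items, list them in the protocol; steps 2 to 4 still apply.

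The cost is four rows on an existing checklist, a short addition to the SAP, and no new visit or instrument. The downside is more adverse-event entries in both arms, some reflecting ordinary fluctuation in behavior. The baseline rating and the placebo arm are there to put those in context.
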